7.2 Adjustments for Covariates

Baseline inflammatory lesion count will be a covariate for the primary efficacy endpoint for inflammatory acne lesion counts. Similarly, baseline non-inflammatory lesion count will be a covariate for the primary efficacy endpoint for non-inflammatory lesion counts. No other covariates are planned to be used in the analyses for this study.

2. Missing values will be filled in '5 x nmiss' times to generate '5 x nmiss' complete data sets. The imputation model used will be the analysis model.
3. For each complete data set, compute the necessary derived variables. Each complete data set will be analyzed with the appropriate analysis model. See Sections 7.3.2.1 and 7.3.2.2 for details.
4. Results from these analyses will be combined into a single inference using SAS PROC MIANALYZE.

7.3.1 MCMC Multiple Imputation

7.3.1.1 Lesion Count Variable Missing Data Imputation

A total of 4 random seeds will be needed to use PROC MCMC to impute inflammatory lesion counts and non-inflammatory lesion counts for the two treatment groups. Those 4 random seeds have been pre-specified by using a random number generator:

- Inflammatory Lesion Counts; Olumacostat Glasaretil Gel, 5.0%: Seed= 1367270369;
- Inflammatory Lesion Counts; Olumacostat Glasaretil Gel, Vehicle: Seed= 197172559;
- Non-Inflammatory Lesion Counts; Olumacostat Glasaretil Gel, 5.0%: Seed= 453193225;
- Non-Inflammatory Lesion Counts; Olumacostat Glasaretil, Vehicle: Seed= 1120886549.

After imputing with PROC MCMC, the absolute change in lesion counts will be computed. Each complete data set will be analyzed with an ANCOVA with factors of treatment group and analysis center and the respective baseline lesion count as a covariate. A factor of treatment group by analysis center will be added if necessary, and appropriate modifications will be made should the analysis be based on a non-parametric method. The results from these analyses will be combined using SAS PROC MIANALYZE.

7.3.1.2 IGA Missing Data Imputation

A total of 2 random seeds will be needed to impute IGA for the two treatment groups. Those 2 random seeds have been pre-specified by using a random number generator:

- IGA; Olumacostat Glasaretil Gel, 5.0%: Seed= 1249913374;
- IGA; Olumacostat Glasaretil Gel, Vehicle: Seed= 1524754873.

After imputing with PROC MCMC, the dichotomous success rate (clear or almost clear with at least a 2-point change from Baseline) will be computed. The 12-week estimated IGA values will be rounded to the nearest integer value prior to evaluating the success rate. Each complete data

set will be analyzed with a logistic regression with factors of treatment group and analysis center. The results from these analyses will be combined using SAS PROC MIANALYZE.

7.3.2 Sensitivity Analyses

7.3.2.1 Lesion Count Variable Missing Data Imputation

The first sensitivity analysis for absolute change in lesion count will use a repeated measures ANCOVA, with factors of treatment group, analysis center, visit (i.e., Week 4, Week 8) and treatment group by visit interaction and a covariate of baseline lesion count. In this analysis, data from all post-baseline visits will be included with no imputation for missing data.

The second sensitivity analysis will use the model-based multiple imputation method to impute missing data for the absolute change in lesion counts at Week 12. The imputation model will include treatment group, analysis center, and baseline lesion count. A total of 2 random seeds will be needed to impute inflammatory lesion counts and non-inflammatory lesion counts for the two treatment groups. Those 2 random seeds have been pre-specified by using a random number generator:

- Inflammatory Lesion CountsSeed= 1342565113;
- Non-Inflammatory Lesion Counts: Seed= 974836051.

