5. CHANGES IN THE CONDUCT OF THE STUDY OR PLANNED ANALYSES

There are no changes in the conduct of the study, but there are minor changes to the planned analyses.

The pooling analysis described in the protocol is updated in the statistical analysis plan (SAP) to reflect the intended analysis. The protocol discusses pooling sites with five or fewer subjects enrolled in each treatment arm. Taking into consideration the randomization ratio, the SAP requires ten subjects in the active treatment arm and five subjects in the vehicle group. The SAP also clarifies the pooling of sites will be performed for each country separately.

As part of the pooling analysis, the treatment effect within investigational site must be investigated. The protocol states the site main effect will be examined by using a one-way analysis of variance (for lesion count variables) or a logistic regression analysis (for dichotomized IGA) with a factor of site. The SAP instead explains site will be incorporated into the primary analysis models. Change from Baseline in lesion counts will be analyzed with an analysis of covariance (ANCOVA) (unranked or ranked) with factors of treatment group, investigational site and treatment group by investigational site interaction, and the respective baseline lesion count variable as a covariate. The dichotomized primary endpoint will be analyzed with a logistic regression with factors of treatment group, investigational site and the interaction term of treatment group by investigational site.

The protocol describes repeated measures sensitivity analyses for the primary efficacy endpoints. Treatment group, analysis center and visit are listed as factors for the repeated measures analyses. In addition to these factors, the SAP includes a factor of treatment group by visit interaction.

The seed values pre-specified in the protocol are the same values as in the parallel executed Phase 3 (DRM01B-ACN03). The seed values were updated to be unique.

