Note that interaction and skewness p-values will be computed for each imputation of multiply-imputed data. Model determination will depend on averaged p-values, computed by finding the mean p-values across all imputations.

The proportion of subjects who are dichotomized to success at Week 12 will be analyzed using a logistic regression with factors of treatment group and analysis center.

The sensitivity analysis for absolute change in lesion count will include a skewness test, based on the methods presented by J.H. Zar (1984) [1]. A ranked repeated measures analysis of covariance with factors of treatment group, visit, analysis center and treatment by visit interaction, and the respective baseline lesion count as covariate will also be included. Values will be ranked across all visits (i.e. visit will be ignored when ranking) and the baseline covariate will not be ranked.

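### The repeated-measures lesion-count sensitivity model uses one baseline slope for all visits, so its Week 12 contrast can be less precise than it need be

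*SAP*

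**What the plan says.** SAP 7.3.2.1 gives the model factors for treatment group, analysis center and visit, together with "treatment group by visit interaction and a covariate of baseline lesion count". Its visit list names only Weeks 4 and 8, yet it adds that "data from all post-baseline visits will be included with no imputation for missing data". The ranked counterpart in SAP 7.9.7.1 has the same structure: "treatment by visit interaction, and the respective baseline lesion count as covariate".

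No baseline-by-visit term appears elsewhere. SAP Section 5, describing the change from the protocol's repeated-measures model, says only: "In addition to these factors, the SAP includes a factor of treatment group by visit interaction". SAP 7.2 closes the list: "No other covariates are planned to be used in the analyses for this study".

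The primary lesion-count analysis is a different model, fitted at Week 12 alone after multiple imputation. Under SAP 7.3.1.1, every imputed data set goes through an ANCOVA on treatment, center and the matching baseline count. Its baseline slope is therefore the Week 12 slope.

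**The concern.** The outcome is absolute change, and a subject who starts with more lesions has more to lose. If improvement builds over 12 weeks, the slope of change on baseline could steepen from Week 4 to Week 12. The SAP lets the treatment effect move with visit but not this slope. A single fitted slope is then a weighted average over visits, and Week 12 is adjusted with a slope that is not its own.

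Two things would follow. The Week 12 interval could be wider than the collected data allow. The model could also leave part of a chance baseline imbalance in the Week 12 difference that the primary ANCOVA would remove. SAP 7.3 says the sensitivity analyses are there to show how much the imputation method matters. A second difference from the primary, in baseline adjustment, blurs that comparison.

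**Working it through.** **1. The plan's own figures.** The documents give no figure for this model, so the nearest check is the sample-size section (SAP 4.2).
- Non-inflammatory, 450/225, difference 14.73 − 9.70 = 5.03, SD 16.72: SE = 16.72 × √(1/450 + 1/225) = 1.365; 5.03/1.365 = 3.68; power 95.8% (95.7% by noncentral t). Stated: 95%.
- Inflammatory, 300/150, difference 15.21 − 9.7 = 5.51, SD 11.00: SE = 1.10; 5.51/1.10 = 5.01; power 99.9%. Stated: at least 95%.

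Both reproduce. At the planned 467/233, non-inflammatory power is 96.3%.

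**2. Formula.** Let β be the true slopes of change on baseline at Weeks 4, 8 and 12, and S the residual covariance across visits. With an unstructured covariance (an assumption, since the SAP names none), the large-sample common slope is

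b = (1′S⁻¹β) / (1′S⁻¹1).

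The Week 12 variance is multiplied by 1 + SD_base² × (β12 − b)² / (Week 12 residual variance). The SE factor is the square root of this.

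**3. Inputs that must be assumed.** The SDs of change (16.72 and 11.00) are from the documents. Baseline SD, slopes by visit and correlations between visits are not given there.

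**4. Central case (inflammatory).** Assumed: baseline SD 10; count SD 11.8 at each visit; correlation of baseline with Weeks 4/8/12 of 0.7/0.6/0.5; adjacent-visit correlation 0.7 and Week 4 with Week 12 0.6. The implied SD of Week 12 change is 11.0, as in the SAP.
- Slopes: 0.7 × 11.8/10 − 1 = −0.17, then −0.29 and −0.41.
- Week 12 residual variance: 11.8² × (1 − 0.5²) = 104.4.
- Weights 0.53/0.25/0.22 give b = −0.255.
- Inflation: 10² × (0.410 − 0.255)² / 104.4 = 2.3% in variance, about 1.2% in SE. This equals about 16 of 700 subjects.

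The non-inflammatory central case (baseline SD 15) also gives 2.3%. Applied to the planning SD for scale, power at 467/233 goes from 96.3% to 96.0%.

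**5. Range.**

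| Assumptions | Week 12 SE increase |
|---|---|
| Equal slopes at all visits | 0 |
| Central case above | about 1.2% |
| Assumed slopes by visit, equal residual SDs | about 0.1–3% |
| Same slopes, residual SDs in ratio 0.75:0.9:1 | about 0.2–9% |
| Baseline correlation falling 0.8/0.6/0.4, visit correlation 0.85 | 13% |

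The third and fourth rows use non-inflammatory baseline SD 15–25 with slopes from −0.20 or −0.30 at Week 4 to between −0.38 and −0.45 at Week 12. For inflammatory lesions they use baseline SD 8–14 with slopes from −0.30 or −0.38 to −0.50. Visit correlations are 0.6–0.75, and 0.1 lower for Week 4 with Week 12. In the last row the variance inflation is 27.7%; non-inflammatory power on the planning SD would be about 91.3%. Inflammatory power stays above 99.9% throughout.

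**6. Chance imbalance in lesions.** With an assumed baseline SD of 20, a one-SE imbalance is 20 × √(1/467 + 1/233) = 1.6 lesions. With slopes −0.20/−0.33/−0.45 and the 0.75:0.9:1 ratio, b is −0.264 to −0.234. The model then leaves (0.45 − 0.264) × 1.6 = 0.30 to (0.45 − 0.234) × 1.6 = 0.35 lesion in the Week 12 difference, against a planned 5.03.

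**7. Bias.** In simulations at 467/233 (300 runs per scenario, center omitted, no dropout or about 15% dropout missing at random), the common-slope and by-visit models gave mean Week 12 differences within 0.05 lesion of each other. Model-based SE ratios were 1.000 with equal slopes, 1.012–1.013 in the central cases and 1.126–1.131 in the adverse cases, in line with the formula.

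**The case against.** The strongest reply is that the loss is conditional. The documents give no baseline SD, no slopes by visit and no correlations. Subjects qualify on at least 20 lesions of each type, so regression to the mean could produce a negative slope as early as Week 4, with little change afterwards. If so, there is nothing to gain. This stands.

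The pull toward earlier visits is also conditional. It needs smaller residual variation at those visits, or baseline correlations that fall over time. With equal residual SDs in the −0.20/−0.33/−0.45 example, the weights are roughly 0.36–0.39, 0.23–0.27 and 0.36–0.39, and the SE loss is about 1.5%. This stands too.

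A reader might infer that the model gives wrong Week 12 predictions for subjects who leave early, and hence a biased treatment difference. The documents do not support that, and the simulations in step 7 showed no bias with about 15% dropout.

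Another sensitivity analysis is free of the constraint: the model-based imputation uses baseline count, treatment group and analysis center for Week 12 change, and then fits the Week 12 ANCOVA. That reduces the importance of the point.

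Finally, the same SAP sentence leaves larger gaps. It lists only Weeks 4 and 8 for the visit factor while including all post-baseline data, and states neither a Week 12 contrast nor a covariance structure. This is correct, and the same edit can address the visit list and the contrast.

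What remains is that the extra term costs almost nothing if slopes are equal and helps if they are not.

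**Conclusion.** The point holds as a minor refinement. The repeated-measures model has one baseline slope for all visits, whereas the primary ANCOVA fits its own at Week 12. If slopes differ by visit, the Week 12 contrast can lose precision and remove less chance imbalance, without bias on average.

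The SE loss is zero with equal slopes, about 1% in the central case, and roughly 9 to 13% only under adverse combinations. All of these rest on assumed baseline SDs, slopes and correlations, on an unstructured covariance, and on a Week 12 contrast being what is reported.

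It would be too strong to say that the model certainly loses precision, or that trial conclusions are at risk. The primary test, the secondary testing order (SAP 7.6), the second sensitivity analysis and the sample size do not use this model.

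**What to change.** In SAP 7.3.2.1, add a baseline-lesion-count-by-visit interaction to the repeated-measures ANCOVA, include Week 12 explicitly in the visit factor, and state that the Week 12 treatment contrast is reported. The same term may be added to the ranked version in SAP 7.9.7.1 for consistency. No gain is claimed there: values are ranked across visits with an unranked baseline, and no calculation covers that scale.

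The cost is one model term and a sentence or two in the SAP. With three visits, the term uses two degrees of freedom, out of at most 700 × 3 = 2,100 observations. No new data are needed. Priority is low.

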7.3.2.2 IGA Missing Data Imputation

The first sensitivity analysis for the dichotomized IGA success will use a repeated measures logistic regression model (generalized estimating equations), with dichotomized IGA success as the dependent variable and treatment group, analysis center, visit (i.e., Week 4, Week 8) and treatment by visit interaction. In this analysis, data from all post-baseline visits will be included with no imputation for missing data.

The second sensitivity analysis will use the model-based multiple imputation method to impute missing data for the dichotomized IGA data at Week 12. The imputation model used will be a logistic regression with factors of treatment group and analysis center. One random seed will be needed to impute IGA for the two treatment groups. The random seed has been pre-specified by using a random number generator:

- IGA: Seed= 318176687.

7.4 Interim Analyses and Data Monitoring

No interim analysis or data monitoring is planned for this study.

7.5 Multicenter Studies

The clinical study will be conducted under a common protocol for each investigational site with the intention of pooling the data for analysis. Every effort will be made to promote consistency in study execution at each study site. The study is intended to be conducted in a manner such that a minimum of 15 subjects will be randomized and included in the ITT population (i.e., at least ten subjects in the active treatment arm and five subjects in the vehicle treatment arm) for any investigator. In the event that there are too few subjects in a treatment arm for an investigational site, then the site's data will be combined with other site's data to achieve the desired sample size minimum per treatment arm. Country will be considered when pooling sites, such that sites from the United States will be combined with other sites from only the United States, and similarly for sites from Canada and sites from Australia. The combining of investigator data will be accomplished by taking the investigator with the smallest enrollment and combining it with the investigator with the largest enrollment, restricted to investigational sites who did not meet minimum enrollment. If there is a further need to combine data, then the data of the investigator with the second smallest enrollment will be combined with the investigator's data which had the second largest enrollment (restricted to investigational sites who did not meet minimum enrollment), and so on. This process will continue for all investigators who did not have a minimum of 15 subjects enrolled. The process of combining investigator data that have insufficient subjects per treatment arm will result in redefining the groups of investigators for the purposes of statistical analyses. These combined groups will be referred to as "analysis centers" in the statistical analyses.

The consistency of treatment response will be investigated across the analysis centers subsequent to combining the data as described above. Statistical tests will be conducted to identify if there are extreme analysis centers that could affect the interpretation of common statistical and clinical conclusions. An analysis center by treatment interaction will be included in the primary and secondary variable analyses to test for parallel treatment effect at an alpha level of 0.10. Change from baseline in inflammatory lesions and non-inflammatory lesions will be analyzed with an ANCOVA (unranked or ranked) with factors of treatment group, analysis center and treatment group by analysis center interaction and the respective baseline lesion count variable as a covariate. For the purpose of testing consistency of treatment response, the dichotomized IGA will be analyzed with a logistic regression with factors of treatment group, analysis center, and the interaction term of treatment group by analysis center. Further examination will follow for any variables that have a significant ANCOVA or logistic regression interaction term.

In the event that the ANCOVA or logistic regression interaction (referred to henceforth as the "appropriate test") p-value is ≤ 0.10 , a sensitivity analysis that excludes analysis centers with the extreme efficacy result will be performed to determine the robustness of the treatment effect. On the other hand, if all three analyses result in interaction terms with p-values > 0.10 , then the

conclusions from the pooled data will be considered to be free of the impact of extreme analysis centers.

The first step in conducting a sensitivity analysis is to identify the extreme analysis center or centers that contribute to the statistical significance of the interaction term of the appropriate test. The process involves submitting subsets of analysis centers to the appropriate test and observing the interaction p-value for the subset. Subsets producing interaction p-values >0.10 are considered homogeneous.

The search for an extreme analysis center begins by analyzing all subsets that can be created by excluding one analysis center. If one or more of the subsets result in an interaction p-value >0.10 , then the analysis center excluded from the subset with the largest interaction p-value is deemed to be the extreme analysis center.

If all subset interaction p-values are ≤ 0.10 , then the process will analyze the interaction for all subsets that can be created by excluding two analysis centers. If one or more of these subsets generate interaction p-values > 0.10 , then the analysis centers excluded from the subset with the largest interaction p-value are deemed the extreme analysis centers.

Thus, the process of identifying the extreme analysis centers will continue in a stepwise manner by first excluding one, then two, then three, etc., analysis centers until the appropriate test interaction p-value is > 0.10 .

Once the extreme analysis center or centers have been identified, then the treatment p-values of the remaining analysis centers will be computed. Inferences will be drawn from the treatment p-value, as well as any pertinent observations regarding the extreme analysis center or centers. Additionally, it is noted that this process excludes subjects from the analysis in a nonrandom manner and has an unpredictable impact on the power of the treatment effect test. In the event that the treatment effect of the remaining subset is not statistically significant, due consideration of the post hoc aspects of the process will be given when the results are interpreted. Conclusions will be presented by the Sponsor as appropriate to the findings of the sensitivity analysis.

Prior to investigating the treatment effect within the analysis centers, the treatment effect within investigational site will be investigated to determine if the site-to-site variability is such that it could mask the analysis center effects. Thus, prior to pooling, change from baseline in inflammatory lesions and non-inflammatory lesions will be analyzed with an ANCOVA (unranked or ranked) with factors of treatment group, investigational site, and treatment group by investigational site interaction, and the respective baseline lesion count variable as a covariate. The dichotomized primary endpoint will be analyzed with a logistic regression with factors of treatment group, investigational site, and the interaction term of treatment group by investigational site. If any of the analyses are not computationally feasible due to some investigational sites having very few subjects enrolled, the low-enrolling investigational sites will be excluded from the analysis.

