I have read this protocol, including the appendices, and agree that it contains all necessary details for carrying out the study as described. I will conduct this protocol as outlined herein, according to the ethical principles that have their origin in the Declaration of Helsinki, International Conference on Harmonisation (ICH) Guidelines for Good Clinical Practice (GCP) and applicable laws, rules and regulatory requirement(s) including those of Canada and the United States (US) Food and Drug Administration (FDA).

I agree to obtain the Institutional Review Board (IRB)/Independent Ethics Committee (IEC) approval of the protocol and informed consent prior to the start of the study.

I agree to obtain formal written informed consent in accordance with applicable federal and local regulations and international guidelines from all subjects prior to their entry into the study.

I have received and reviewed the Investigator's Brochure including the potential risks and side effects of the product and instructions for use.

I agree to report to the Sponsor any adverse events that occur during the course of the study in accordance with the ICH GCP guideline and the protocol.

I agree to ensure that all associates, colleagues, and employees assisting me with the conduct of the study are informed of their responsibilities in meeting the above commitments and the commitments set forth in the Investigator's Agreement.

I agree to maintain adequate and accurate records and to make those records available for inspection in accordance with the ICH GCP guideline, and federal and local requirements.

I understand that the study may be terminated or enrollment suspended at any time by the Sponsor, with or without cause, or by me if it becomes necessary to protect the best interests of the study subjects.

nvestigator's Signature	Date (DD MMM YYYY)
nvestigator's Name (print)	

06 October 2016 Page 4 Confidential

PROTOCOL SYNOPSIS

	-	
Title:	A Randomized, Double-Blind, Vehicle-Controlled, Efficacy and Safety Study of Olumacostat Glasaretil Gel in Subjects with Acne Vulgaris	
Protocol Number:	DRM01B-ACN04	
Phase:	3	
Number of Sites:	Approximately 50	
Study Population	Subjects ≥ 9 years of age with acne vulgaris	
Sample Size	Approximately 700 subjects	
Study Treatment	Olumacostat Glasaretil Gel, 5.0%, applied twice daily Olumacostat Glasaretil Gel, Vehicle, applied twice daily	
Randomization	2:1 (active:vehicle)	

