11.3 Primary Efficacy

Absolute change from baseline to Week 12 in inflammatory and non-inflammatory lesion counts will be analyzed using either parametric or non-parametric methods consistent with the statistical assumptions required to support the analyses. Specifically, the tests of superiority will be based on an ANCOVA with factors of treatment and analysis center and the respective Baseline lesion count as a covariate or on ranked data submitted to an ANCOVA with factors of treatment and analysis center and the respective Baseline lesion count as a covariate. If the treatment-by-

analysis center interaction effect is significant at an alpha less than 0.10, then the effect will be included in the model; otherwise it will be removed.

A skewness test, based on the methods presented by J.H. Zar (1984) [14], will be applied to the residuals resulting from an ANCOVA. A two-sided p-value for the skewness test significant at 0.01 will imply the use of the non-parametric method. If a parametric analysis is indicated, the results of the parametric analysis will be considered the primary analysis. Should a non-parametric analysis be indicated, the absolute or percent changes in inflammatory and non-inflammatory lesions will be rank transformed prior to submitting them to the ANCOVA. Results of the rank-transformed analyses then will be considered the primary analysis; however, results of the non-ranked transformed analyses will also be presented.

The proportion of subjects who are dichotomized to success at Week 12 will be analyzed using the logistic regression test stratified by analysis center.

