4.1.2 Method of Assigning Subjects to Treatment Groups

A randomization schedule will be generated by a member of the Statistical Services department at QST Consultations, Ltd. (QST) who is not associated with the conduct or analysis of the study, using a validated system. The randomization list will not be stratified but stratification by site will be completed within the Interactive Web-based Randomization System (IWRS).

At the Baseline/Day 1 visit, qualified subjects will be randomized to treatment using the IWRS. The IWRS will assign a study drug kit number based on the subject's treatment assignment and available inventory at the investigational site. The kit number will be recorded in the electronic case report form. Approximately 467 subjects will be randomized to active treatment and approximately 233 subjects will be randomized to vehicle treatment for a total of approximately 700 subjects. Subjects will be randomized to treatment groups in such a manner to balance treatment allocation within study sites in a 2:1 fashion.

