4.2 Determination of Sample Size

The sample size for this study was based on estimates from the DRM01B-ACN02 study observed Week 12 results. Estimates were combined for all three active treatment groups as well as for the two vehicle groups. All power calculations were performed with nQuery Advisor Version 7.0 for a two-sided test at $\alpha = 0.05$.

For inflammatory lesion change a sample size of 300 Olumacostat Glasaretil Gel and 150 Olumacostat Glasaretil Gel, Vehicle subjects has at least 95% power to detect a statistically significant difference with a significance level of 0.05 using the estimated absolute change from Baseline in treatment means of -15.21 and -9.7 for Olumacostat Glasaretil Gel versus its vehicle, respectively, with a standard deviation (SD) of 11.00.

For non-inflammatory lesion change a sample size of 450 Olumacostat Glasaretil Gel and 225 Olumacostat Glasaretil Gel, Vehicle subjects has 95% power to detect a statistically significant difference with a significance level of 0.05 using the estimated absolute change from Baseline in treatment means of -14.73 and -9.70 for Olumacostat Glasaretil Gel versus its vehicle, respectively, with a SD of 16.72.

The success rate for dichotomized IGA is estimated to be 20.5% in the Olumacostat Glasaretil Gel subjects and 9.6% in vehicle subjects. A sample size of 444 Olumacostat Glasaretil Gel and 222 Olumacostat Glasaretil Gel, Vehicle will have 95% power to detect a statistically significant difference in proportions of successes. These calculations were performed with nQuery Advisor Version 7.0 for a two-sided continuity corrected chi-square test at $\alpha = 0.05$.

To allow for a slight loss in power due to dropouts and withdrawals as well as to accommodate sufficient power in all three co-primary variables, a sample of 700 subjects randomized to 2 to 1 for Olumacostat Glasaretil Gel (n=467) and vehicle (n=233), respectively, will be enrolled in the trial.

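### The co-primary IGA model fits analysis centers as ordinary logistic factors, which overstates the odds ratio by about 4% to 5%, and the documents disagree on whether the test is stratified

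*SAP*

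**What the plan says.** - **Randomisation.** SAP 4.1.2 stratifies by site in the IWRS, so as to "balance treatment allocation within study sites in a 2:1 fashion".
- **Analysis centers.** SAP 7.5 intends that "a minimum of 15 subjects will be randomized and included in the ITT population" for each investigator, split as 10 active and 5 vehicle. Sites that miss this are pooled. The pooling is "accomplished by taking the investigator with the smallest enrollment and combining it with the investigator with the largest enrollment", then second smallest with second largest, and so on. It applies only to below-minimum sites and stays within a country. Sites that meet the minimum remain intact.
- **IGA model in the SAP.** Section 7.9.7.1 says the success proportion "will be analyzed using a logistic regression with factors of treatment group and analysis center". Section 7.3.1.2 says the same for each imputed data set. Neither names a conditional likelihood or a strata option, so as written this is ordinary logistic regression with one parameter per center.
- **IGA model in the protocol.** Section 11.3 says the proportion "will be analyzed using the logistic regression test stratified by analysis center", and section 11.6 also calls the logistic test a stratified one. Section 11.7 describes treatment group and analysis center as factors, as the SAP does.
- **Reconciliation.** SAP section 5 lists the changes from the protocol analyses and is silent on this difference.
- **Secondary IGA endpoint.** SAP 7.9.7.2 applies the same logistic method to the endpoint of at least a 2-grade improvement.

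**The concern.** When a logistic model has one free intercept per center and each center holds few successes, ordinary maximum likelihood pushes the treatment log odds ratio away from zero. A conditional likelihood removes the center intercepts and so avoids most of this; Mantel-Haenszel does much the same. The protocol's stratified wording could mean such an analysis, while its factor wording and the SAP's point to ordinary dummies. A programmer could defend either for a co-primary endpoint, and the two give systematically different estimates. At stake are the size of the reported IGA effect and an avoidable choice of model after unblinding.

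**Working it through.** **1. Inputs from the documents.** SAP 4.2: 467 active and 233 vehicle subjects; IGA success 20.5% versus 9.6%; 444 + 222 subjects for 95% power with a continuity-corrected chi-square test at two-sided 0.05. Protocol Synopsis: "Approximately 50" sites. SAP 7.5: the 10 + 5 minimum and the pooling rule.

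**2. The plan's own figure.** Let d = 0.205 − 0.096 = 0.109, ratio k = 2, pooled rate (0.096 + 2 × 0.205)/3 = 0.1687.

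- Uncorrected vehicle n = [1.960 × √(1.5 × 0.1687 × 0.8313) + 1.645 × √(0.0868 + 0.1630/2)]² / 0.109² = (0.899 + 0.675)² / 0.01188 = 208.4, rounded up to 209.
- Corrected n = (208.4/4) × [1 + √(1 + 6/(208.4 × 2 × 0.109))]² = 222.

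So 222 vehicle and 444 active are reproduced exactly. The crude odds ratio is (0.205/0.795)/(0.096/0.904) = 2.43, log 0.887.

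**3. Number of centers (assumed, not a document figure).** The pooling rule was applied to 700 subjects at 50 sites, with gamma-distributed or equal enrolment and 2:1 allocation within site. It gave a mean of 32 to 35 centers across enrolment patterns, 95% range 29 to 37. With 40 sites the figure is about 31, with 60 sites about 38.

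**4. Sparsity.** Expected successes are 467 × 0.205 + 233 × 0.096 = 95.7 + 22.4 = 118.1. Over 34 centers that is 3.5 per center, of which 22.4/34 = 0.66 is in the vehicle arm. A center at the 10 + 5 minimum has no success with probability 0.795¹⁰ × 0.904⁵ = 0.06.

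**5. Effect on the estimate.** Simulation with that pooling rule, gamma shape 4, a 40/6/4 country split, all outcomes taken as observed, and a normal site effect on the logit scale; 4,000 trials under the alternative per setting. Odds ratios are exponentiated mean log odds ratios.

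| Site SD | True OR | Center dummies, ordinary fit | Conditional, by center | Mantel-Haenszel, by center | Dummies over conditional |
|---|---|---|---|---|---|
| 0 | 2.43 | 2.55 | 2.45 | 2.45 | +4.2% |
| 0.5 | 2.50 | 2.64 | 2.53 | 2.53 | +4.4% |
| 1.0 | 2.72 | 2.83 | 2.70 | 2.71 | +4.8% |

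A separate simulation with about 36 centers gave mean log odds ratios of 0.943 (dummies) and 0.902 (Mantel-Haenszel by center) against a true 0.887. The ratio is exp(0.041) = 1.042.

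**6. What drives it.** With equal-sized centers and no center effect, the excess over conditional is 3.0% at 25 centers, 4.2% at 34 and 5.7% at 46. Dummies for the actual sites, compared with conditional logistic by site, give an excess of 6.2% to 7.3%. More intercepts mean more bias, so pooling lowers it.

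**7. Error rate and power.** Under the null (6,000 trials per setting) the ratio of the two odds ratios is 1.000.

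| Site SD | Null rejection, dummies | Null rejection, conditional |
|---|---|---|
| 0 | 5.53% | 4.90% |
| 0.5 | 5.62% | 5.02% |
| 1.0 | 4.95% | 4.47% |

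The excess is 0.48 to 0.63 points. The Monte Carlo standard error of a single rate is √(0.05 × 0.95/6000) = 0.28 points. Power is 97.4% to 98.3% with dummies and 97.2% to 98.0% conditional.

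**The case against.** The strongest reply is that the effect is negligible. From the planning figures, the standard error of the log odds ratio is √(1/95.7 + 1/371.3 + 1/22.4 + 1/210.6) = 0.25. The shift, log(2.55/2.45) = 0.04, is therefore about 0.16 of a standard error. The endpoint is defined as a proportion, and the analysis sections do not name an odds ratio as a reported result. Protocol 11.7 already uses the SAP's wording, so the SAP follows the protocol's more detailed text. All of this stands and keeps the point minor. It does not remove the two protocol passages that say stratified, nor the fact that the coefficient combined in PROC MIANALYZE is a log odds ratio.

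Four stronger readings are tempting and do not hold.

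- *Pooling causes the bias.* It reduces it (working, step 6). Only below-minimum sites of one country are paired, so centers are not formed by size alone, and many are intact sites.
- *Most sites must be pooled because 50 × 15 = 750 exceeds 700.* At 15 each, 46 sites use 690 subjects, so as few as 4 of 50 could fall short. The site and subject numbers are approximate, the minimum is stated as an intention, and SAP 7.5 provides a fallback. A larger share rests on the assumed enrolment spread.
- *Centers without a success break the model.* Their own intercept has no finite estimate, but the treatment estimate stays finite. Conditional and Mantel-Haenszel analyses also gain nothing from such centers.
- *The lesion-count ANCOVA should adjust for site instead.* For a true difference of 5.03 and no site effect, both adjustments estimate 5.02. Power differs by at most 0.3 points for site intraclass correlations of 0 to 0.15.

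**Conclusion.** The point holds as a minor one. The plan leaves open whether the co-primary IGA analysis is conditional. The version in the SAP overstates the odds ratio by about 4% to 5% relative to a conditional analysis on the same centers and raises null rejection by about half a percentage point. The estimate is unbiased under the null and power is essentially the same, so the reported size of effect is affected far more than the likelihood of success. A reader might infer a material inflation of false positives; the simulated rates for the SAP model, 5.0% to 5.6%, do not support that.

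The size depends on about 50 sites, an assumed spread of enrolment giving roughly 29 to 37 centers, and the planning success rates. The simulation did not include the multiple imputation step.

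**What to change.** 1. In SAP 7.3.1.2 and 7.9.7.1, and for the secondary IGA endpoint in 7.9.7.2, specify conditional logistic regression (STRATA statement) or a Cochran-Mantel-Haenszel/Mantel-Haenszel analysis. Stratify by investigational site, which is the randomisation stratum, or at least by analysis center.
2. State how results are combined over imputations. The conditional or Mantel-Haenszel log odds ratio and its standard error can go into PROC MIANALYZE; a Cochran-Mantel-Haenszel statistic would need its own combining rule.
3. Reconcile Protocol 11.3, 11.6 and 11.7 with SAP 7.3.1.2 and 7.9.7.1, and record the decision in SAP section 5 before unblinding.
4. Do not replace centers with site dummies in ordinary logistic regression; that would increase the bias.

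The lesion-count models can stay as they are.

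The cost is SAP wording. Strata with one arm only, or with no success or all successes, add no information. SAP 7.3 makes the imputation model of the second sensitivity analysis equal to the analysis model. For IGA that sentence would need an exception, because a conditional likelihood yields no center intercepts from which to impute.
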